6.2 Handling of Dropouts or Missing Data

6.2.1 Analysis Endpoints

6.2.1.1 Efficacy Endpoints

Refer to Section 3.1 and 3.2 for the list of primary and secondary efficacy endpoints and Section 3.2.1 for the list of secondary endpoints used in the hierarchical analysis.

Bladder diary: For data collected from the 7-day bladder diary, if there is 1 or 2 days with no data, the arithmetic means recorded (on the 5 or 6 days that do have events recorded) from the bladder diary parameters will be used for the days with no recorded bladder diary data. If there are more than 2 days of missing data, then the 7-day bladder diary data will be considered invalid.

Statistical Analysis Plan

Version: Final v2.0

September-2018

Ipsen Protocol No. D-FR-52120-222

000000146259

Date of Issue: 21-

Covance Study ID:

Primary efficacy endpoint: No imputation is planned for the primary analysis of the primary endpoint. A sensitivity analysis of the primary efficacy endpoint will be performed using multiple imputations (MI) for missing or invalid data (see Section 7.6.4.3).

Urodynamic secondary efficacy endpoints: All urodynamic data will be reviewed by independent central reviewers to determine the final values for the urodynamic parameters. Only the central reader urodynamic values will be used for analysis purposes. For the secondary efficacy endpoint of Vol@1stIDC, subjects who do not exhibit a post-treatment IDC at Week 6 after the first IMP administration will have Vol@1stIDC imputed using the recorded corrected MCC volume at Week 6.

Quality of life secondary endpoints: For I-QoL total summary score, in accordance with the I-QoL User's Manual (US English version, March 2013), if no more than three items are omitted, a normal arithmetic mean substitution will be computed for these omitted items and imputed to calculate the total summary score. If more than three items are omitted, then there will be no more imputation for those omitted items, and the total summary score will be missing. Similarly, this rule will be applied for each of the domain scores (avoiding and limiting behavior, psychosocial impact, and social embarrassment). These derived scores will be used for analysis, and the investigator recorded eCRF I-QoL total summary score, and each recorded domain score will only be listed.

The formula for the derived scale scores is as follows:

Scale Score = $\{(\text{the sum of the items} - \text{lowest possible score}) / \text{possible raw score range}\} * 100$

For continuous endpoints analysed by mean or mean change values, inference will be done using mixed-models repeated measures, which assumes that missing outcomes are missing at random (MAR).

6.2.1.2 Safety Endpoints

In general, all available data from subjects who have prematurely discontinued from the study will be used for analysis. For AEs with missing information for the intensity and causality, it will be represented as a missing category.

6.2.2 Missing or Partial Date

In all listings, missing or incomplete dates will be left as they have been recorded. However, for calculation / sorting / assignation based on dates, the following methods will be used:

- (1) If the onset date of an AE/concomitant medication is missing / incomplete, it is assumed to have occurred during the study treatment phase (i.e. a treatment-emergent adverse event (TEAE) for AEs) except if the partial onset date or stop date indicates differently.
- (2) A missing / incomplete date of medical history or disease diagnosis will be assumed to have occurred before any study treatment. For calculation purposes, if only the year is available, then the first day of January will be used to impute, if only the day is missing then the first day of the month will be used to impute.
- (3) An AE could be assigned to several possible treatment cycles according to its partial onset date and stop date. If only the AE start day is missing, then the AE will be assigned to that treatment cycle that includes the first day of that month. If the AE start date has a missing month, then January will be used. An AE with missing start date will be assigned to each

treatment cycle before its end date. The Analysis Data Model programming specifications will outline the rules in more detail. During the study, examples of date imputations will be shared with the team to ensure AE assignment to treatment cycles are in agreement with the team.

- (4) In calculations with date of the first IMP administration, if missing, the date of randomisation will be used.

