1.6 Population to be Studied

This study will recruit adult subjects with UI caused by NDO due to either SCI or MS, who have not been adequately managed with oral medication.

In order to ensure a homogenous population of subjects with SCI and MS for efficacy and safety assessments, all subjects will be required to be routinely performing CIC to manage bladder function, prior to study entry. This is also expected to reduce the risk of urinary tract infection

(UTI) due to impaired voiding following BTX-A treatment, which is observed in subjects not performing CIC.

In addition to BTX-A bladder-naive subjects who have never previously received intradetrusor BTX-A for UI, the study will also enrol BTX-A bladder-non-naive subjects, who have previously received intradetrusor BTX-A for NDO. This will reflect real world usage and it has been demonstrated previously that treatment response does not vary significantly following retreatment in subjects treated with intradetrusor BTX-A for UI due to NDO [18]. In order to be eligible for entry into the study, more than 9 months must have elapsed since any previous intradetrusor BTX-A treatment administration.

1.7 Placebo Usage During Treatment 1

The use of placebo during the first IMP treatment administration ensures a rigorous, scientifically appropriate study design to assess the efficacy and safety of Dysport® in the treatment of UI due to NDO. The use of placebo is justified because:

- Although UI due to NDO is a symptomatic condition, which can lead to significantly impaired quality of life, it is not life-threatening. Therefore, a single administration of placebo with the opportunity to receive active IMP treatment from as early as 12 weeks later ensures that all subjects have the opportunity to receive the active IMP without prolonged delay. All further study treatment administrations will be active IMP, for up to 2 years post randomisation, ensuring all subjects also have the opportunity to be treated with active IMP multiple times during the study, if required.
- Treatment with BTX-A may be associated with an increased risk of UTIs in an NDO population that is already susceptible to UTIs. In order to accurately estimate the true incidence of UTIs associated with the active IMP, compared to the background incidence and the incidence due to the treatment administration procedure, a placebo group comparison is required.

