5.2.6 Retreatment Visit

The Retreatment Visit should ideally be performed within 14 days of confirmed eligibility for retreatment.

It may be performed on the same day as the Retreatment Assessment Visit only if urine culture was taken and prophylactic antibiotics (empiric or adapted) were commenced at least 3 days prior to the combined visit.

The suggested order of procedures for Retreatment Visit is shown in [Table 16](#).

Table 16 Order of Procedures for Retreatment Visit

Suggested order of procedures	Comment	Details of procedure
1. Concomitant medications and therapies		Section 5.2.2.2 Section 6.4
2. Concomitant treatments for NDO		Section 6.4.2.1
3. Retreatment criteria	Confirm subject still meets all retreatment criteria.	Section 4.3
4. Adverse events	Timing of adverse event (pre- or postretreatment) must be recorded.	Section 8.1
5. Vital signs	Must be performed prior to and approximately 30 minutes after treatment administration.	Section 8.4
6. Urine pregnancy test	Must be performed prior to commencing IMP reconstitution in females of childbearing potential. If positive then subject must not receive retreatment.	Section 8.2.5
7. IMP administration	Must be performed only: 
 • If all retreatment criteria are met • If prophylactic antibiotics were commenced 3 or more days prior • If the subject does not have any symptoms suggestive of a UTI • If medications with anticoagulant effects were stopped at least 3 days earlier. Subjects to be observed for at least 30 minutes following administration.	Section 6 Section 6.2.1 Section 6.2.2 Section 6.3 Section 6.3.1

IMP=investigational medicinal product; NDO=neurogenic detrusor overactivity; UTI=urinary tract infection.

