6.3.3 Post-treatment Observation

Vital signs should be recorded approximately 30 minutes following the procedure.

If sedation or general anaesthesia was used then post-treatment observation must also be performed according to local site practice (e.g. monitoring of BP and HR until recovered).

For any AEs that occur on the day of treatment/retreatment it should be clearly documented if the AE occurred before or after the treatment procedure.

All subjects must be observed for a minimum of 30 minutes following the IMP administration. Subjects should only leave the clinic when it is safe and appropriate, according to the investigator's judgement and local site practice.

Subjects should be instructed to contact the site if there are any AEs post-treatment.

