7.7.1 Adverse Events

All AEs will be coded by Sponsor using MedDRA v21.0 (March 2018); (the latest version if updated during the study), and will be classified by MedDRA preferred term and system organ class.

A TEAE is defined as any AE with start date/and time at or after the date/and time of the first dose of IMP, or any AE with start date/and time prior to the date/and time of the first dose of IMP whose intensity worsens at or after the date/time of the first dose of IMP. The Pre-treatment AE is defined as any AE with start date/and time prior to the first dose of IMP administration in DBPC Cycle, and after the date of informed consent.

All TEAEs will be assigned to either DBPC Cycle and/or Dysport Cycle X based on the start date and time, or intensity increase date. For example, for presentation of TEAEs by Dysport Cycle, if the start time/intensity increase time of TEAE is at or after the time of treatment administration of Dysport Cycle X, Day 1 and prior to the time of treatment administration of Dysport Cycle X+1, Day 1, the TEAEs will be assigned to Dysport Cycle X.

In this study, an AESI is for Dysport is TEAEs that suggest a possible remote spread of effect of the toxin or events suggestive of hypersensitivity like reactions. TEAEs due to possible remote spread of the effects of Dysport will be identified using the list of MedDRA PTs compatible with the mechanism of action of BTX-A and based on the recommendations from the Committee for Medicinal Products for Human Use (CHMP) and the Food and Drug Administration (FDA). TEAEs potentially representing hypersensitivity reactions will be identified using the Standardised MedDRA Query (SMQ) (narrow search query) for hypersensitivity reactions. A list of MedDRA preferred terms, used to identify any potential AESI, is provided in Appendix VI.

Statistical Analysis Plan

Version: Final v2.0

September-2018

Ipsen Protocol No. D-FR-52120-222

000000146259

Date of Issue: 21-

Covance Study ID:

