- any UTI TEAEs
 - UTI TEAEs leading to withdrawal
 - serious UTI TEAEs
- TEAE leading to death

In view of the anticipated difference in duration of the Dysport and placebo treatment cycles, this overview table will also be provided including only TEAEs occurring any time after first dose of IMP until up to 12 weeks after first IMP treatment administration.

A similar overview table will be produced for the number and percentage of subjects with at least one of the following events occurred pre-treatment for randomised subjects. The number of occurrences of the following events will be presented as well.

- any AE
 - Intensity of AE (mild, moderate, severe)
- any SAE
 - any SAEs leading to withdrawal
- AE leading to death

TEAEs will be summarised overall, for DPBC cycle, and Dysport Cycles with the number and percentage of subjects with TEAEs presented by primary SOC and PT. In addition, this table will be provided including only TEAEs occurring up to 12 weeks after first IMP treatment administration. This will also be summarised by aetiology of NDO.

The same summaries for overall, for DBPC Cycle, and Dysport Cycles with the number and percentage of subjects with TEAEs presented by primary SOC and PT will be presented for serious TEAEs, IMP-related TEAEs, TEAEs leading to withdrawal, TEAEs of special interest, and other protocol defined TEAEs. TEAEs with PTs observed in $\geq 1\%$, $\geq 2\%$, and $\geq 5\%$ of subjects and IMP-related TEAEs with PTs observed in $\geq 1\%$, $\geq 2\%$, and $\geq 5\%$ of subjects will be summarised as well.

Additionally, TEAEs will be tabulated by decreasing overall PT frequency and intensity in each SOC and PT category.

The above will also be presented for SAEs.

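### SAP 6.2.2 rule (3) counts an adverse event with a missing start day in the previous cycle when it began after a mid-month retreatment

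*SAP*

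**What the plan says.** SAP 6.2.2 rule (3) accepts that a partial date may be compatible with several treatment cycles, and then fixes one. If only the start day is missing, "the AE will be assigned to that treatment cycle that includes the first day of that month". It does not compare the recorded month with the month of a retreatment.

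Nearby rules work differently:

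- SAP 7.7.1, for known dates: "All TEAEs will be assigned to either DBPC Cycle and/or Dysport Cycle X based on the start date and time", or on the date intensity increased. An event at or after an injection belongs to the cycle that injection opens.
- SAP 6.2.2 rule (1): an event with an incomplete onset date is presumed treatment-emergent unless the partial dates show otherwise.
- SAP 6.2.2 rule (3), wholly missing start date: the event is counted in each cycle before its end date.

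Further detail is deferred: "The Analysis Data Model programming specifications will outline the rules in more detail". In addition, "examples of date imputations will be shared with the team to ensure AE assignment to treatment cycles are in agreement with the team".

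**The concern.** Under rule (3), an event known to have started in the month of a retreatment is counted before the injection even if it followed it. An event with no start date at all can still be counted in the later cycle, so the better-recorded event gets the less cautious attribution.

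This matters most when placebo subjects first receive Dysport. The planned numbers in sequences 3 and 4 are 55 + 55 = 110 of 330. For them, a misassigned event moves from Dysport Cycle 1 into the placebo column of the DBPC tables. Protocol 1.7 justifies the placebo arm partly by the need to estimate urinary tract infections due to the active product: "compared to the background incidence and the incidence due to the treatment administration procedure, a placebo group comparison is required". Counting post-Dysport infections under placebo blurs that comparison. In subjects already on Dysport the dose group stays right and only the cycle is wrong.

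**Working it through.** The plan gives no figure to reproduce, so the check applies the rule to dates and then counts cases.

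**1. Which cycle receives the event.** Retreatment needs more than 84 days since the previous administration (SAP 2.2). The first of the retreatment month is at most 30 days before the injection. It therefore lies in the immediately preceding cycle, unless the injection was on the 1st.

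**2. Example (assumed dates).** Day 1 is 10 January 2018 and retreatment is 15 June 2018.

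| True onset, day missing | True cycle | Rule (3) |
|---|---|---|
| 5 June | DBPC | DBPC |
| 18 June | Retreatment | DBPC (wrong) |
| 29 June | Retreatment | DBPC (wrong) |
| 3 July | Retreatment | Retreatment |

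Only onsets in the injection month are affected.

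**3. Share of post-injection events affected.** Assume a 30-day month with injection day and onset day each uniform.

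- Pairs with onset after the injection day: 30 × 29 / 2 = 435.
- The 29 pairs with injection on the 1st are assigned correctly, so 435 − 29 = 406 are misassigned.
- 406 / 435 = 93%. The 2016–2020 calendar gives 25154 / 26921 = 93%.

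That figure is conditional on onset in the same month. Suppose instead that onset is uniform over a window starting on the injection day, averaged over calendar retreatment dates. The misassigned share is then 87% for a 7-day window, 75% for 14 days, 52% for 28 days and 18% for 84 days.

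**4. Current rule against the amended rule.** Events on the treatment day are left out, because their day should be known. There are 435 pairs with onset before the injection and 435 after it. Let r be the post/pre-injection rate ratio among day-missing events. The documents give no value for r.

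- Misassigned now: 406r / (435r + 435).
- Misassigned with the fix, no help from records: 435 / (435r + 435).
- Break-even: r = 435 / 406 = 1.07.

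| r | Now | With fix |
|---|---|---|
| 1 | 406/870 = 46.7% | 435/870 = 50.0% |
| 2 | 812/1305 = 62.2% | 435/1305 = 33.3% |

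If the records identify a share s of the pre-injection events, break-even falls to 1.07 × (1 − s). For example, it is 0.80 at s = 25% (an illustration only).

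**5. The 12-week tables.** Twelve weeks after the first administration is Day 85, and the earliest retreatment is Day 86. A later event could enter these tables only if the imputed first-of-month date were used for the window and fell on or before Day 85. The retreatment would then be on Day 84 + 31 = 115 at the latest. The share of 2016–2020 Day 1 dates for which this is possible is 97% for retreatment at Day 86, 51% at Day 100, 5% at Day 114 and none from Day 116. Rule (3) assigns a cycle; it does not say that the imputed date feeds this window.

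**The case against.** The strongest reply is that first-of-month assignment is a pre-specified convention, and that a later-cycle convention only produces the mirror-image error. This stands in part. With r = 1 and no usable records, the current rule is slightly better (46.7% against 50.0%).

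The value of r is also uncertain. It must be the ratio among day-missing events. Contacts at Weeks 1, 2 and 4 follow an injection, whereas routine contacts before it are 12-weekly plus the assessment visit, so days may be missing more often before the injection. Against that, the documents point to more events after it. Protocol 1.7 recognises infections due to the procedure, Protocol 1.4 lists procedural pain and muscular weakness, and Protocol 8.1.2.11 places toxin-spread symptoms hours to weeks after injection.

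The before/after records help less than they might seem to. Protocol 5.2.6 says "Timing of adverse event (pre- or postretreatment) must be recorded" and Protocol 6.3.3 says "it should be clearly documented if the AE occurred before or after the treatment procedure". Both mainly concern events on the treatment day. Stop dates and the visit of first report are the likelier sources for earlier events.

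Mitigations exist. Missing data are queried (Protocol 11.5, 13.2), and listings keep dates as recorded and show the assigned cycle. Because cycle lengths differ, SAP 7.7.1 adds that "this overview table will also be provided including only TEAEs occurring any time after first dose of IMP until up to 12 weeks" after first treatment; that table includes urinary tract infections. The programming specifications might refine the rule, but more detail does not reverse a stated rule, and reviewing examples is not itself a rule.

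**Conclusion.** The point holds and is minor. As written, rule (3) moves a day-missing event that began after a retreatment, in the same calendar month and with the injection later than the 1st, into the preceding cycle. That is at odds with onset-based assignment in SAP 7.7.1 and less cautious than the two neighbouring defaults.

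Its reach is limited. Onsets in later months are assigned correctly. The number of day-missing events is not given and, with frequent contacts after each injection, is probably small. Safety analysis is descriptive (Protocol synopsis, Statistical methods). Events of special interest are selected by medical review that considers time since last treatment, so only the cycle they are counted in is affected.

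A reader might infer that the placebo comparison will be materially distorted and Dysport's risks understated. The documents do not support that. No event count is available, and the DBPC Dysport columns can gain post-retreatment events from sequences 1 and 2 in the same way, so the net effect is not established. A reader might also take the 93% as the error rate for all day-missing events. It applies only to same-month onsets after the injection day. Nor can the final assignments be judged, because the programming specifications are not among the documents.

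The percentages assume uniform days, and the case for the amended rule rests on r exceeding about 1.07, or less where records identify earlier events.

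**What to change.** Amend rule (3) as follows. If the known onset month contains a retreatment, assign the event to the cycle that starts with that injection, unless one of these places it before the injection: the stop date, the visit at which it was first reported, or a before/after-procedure record where one exists. Otherwise keep the first-of-month rule. Carry the same wording into the programming specifications. Report how many adverse events had a missing start day and how many change cycle under the amended rule; this will show whether the issue touched the tables.

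The cost is one or two sentences of SAP text and a small programming change before database lock. The downside is that some events truly before the injection will move to the later cycle, which can lower DBPC counts, including in the Dysport columns.

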7 STATISTICAL METHODS

7.1 General Principles

All data processing, summarisation and analyses will be performed using the SAS Environment / Version 9.4 (or later) of the SAS® statistical software package.

All data collected during the study will be presented in listings without any imputation by treatment group, subject, assessment and visit (where applicable), unless otherwise specified.

Data will be presented in summary tables by treatment group (as described below), assessment and visit (where applicable).

Overall, the analysis strategy is to evaluate efficacy and safety data from the initial DBPC Cycle and to evaluate efficacy and safety over repeated Dysport treatments, using analyses by Dysport Cycle (Dysport Cycle 1, 2...etc.), as illustrated in schematic diagram later in this section. In general, tables associated with the DBPC Cycle will be separate from the tables assessing repeat treatment with Dysport which are presented by Dysport Cycle:

- During analysis of the DBPC (DBPC cycle), data will be displayed using the following treatment group labels, in the order presented:
 - Placebo
 - Dysport 600 U
 - Dysport 800 U
 - All Dysport
- During analysis by Dysport Cycle, data will be displayed by number of Dysport treatments (see diagram below) using the following treatment group labels:
 - Dysport Cycle 1
 - Dysport 600U
 - Dysport 800U
 - All Dysport
 - Dysport Cycle 2
 - Dysport 600U
 - Dysport 800U
 - All Dysport
 - Dysport Cycle X

Statistical Analysis Plan

Version: Final v2.0
September-2018
Ipsen Protocol No. D-FR-52120-222
000000146259

[figure not shown]
Date of Issue: 21-
Covance Study ID:

- Dysport 600U
- Dysport 800U
- All Dysport

Analysis of Dysport Cycle 1 will therefore include (see diagram below):

- Data from subjects who received a Dysport treatment after having initially received placebo as their first study treatment on Day 1 i.e. will only use data from their first Dysport treatment,
- Data from subjects who received Dysport as their first study treatment on Day 1

Schematic diagram summarising concept of Dysport Cycles:

Descriptive summary statistics for continuous variables will include the number of subjects (n), mean, standard deviation (SD), median, minimum and maximum.

Descriptive summary statistics for categorical variables will include frequency counts and percentages [n (%)]. The denominator for percentage calculations will be the number of subjects in the analysis population for the designated treatment cycles. Unless stated otherwise in the table shells (e.g. for the TEAE of MS relapse, the denominator only relates to the number of MS subjects),

Dates will be displayed as DDMMYYYY.

Overall, in the statistical tables the category “Missing” will be presented if the number missing is > zero for at least one treatment group.

Unless otherwise specified, the eCRF recorded strata (i.e. the correct strata) will be analysed for all used in all the data displays.

